## **METHODS: MONITORING**

## **21.a Data Monitoring**

By monitoring we mean the act of supervising the progress of a clinical trial, and ensuring that it is conducted and reported in accordance with the protocol, the Standard Operating Procedures (SOPs), the Good Clinical Practice (GCP), the Good Manufacturing Practice (GMP) and applicable regulations. The purpose is to verify that:

- The rights and health of human subjects are respected
- The data reported is accurate, complete and verifiable on source documents
- The conduct of the trial complies with the approved protocol / amendments / GCP / GMP / and requests from regulatory authorities
- The quality of the trial is verified over time

Monitoring will be carried out by the respective CTUs (Clinical Trial Units) at the sites or by the CRO delegated for this purpose.

A monitoring plan and SOPs describing in detail the documents and data to be monitored will be developed to ensure homogeneous monitoring.

An initiation visit before the start of the trial, visits during and at the end of the trial (close-out visit) are provided for each center. Regular telephone conferences between the CTUs / CROs will ensure the harmonization of procedures.

All data and source documents will be made accessible to the monitors and any questions posed during monitoring can be answered by any participant.

### **Data Monitoring Committee (DMC)**

The DMC will consist of an independent group of 3 experts consisting of a clinical cardiologist expert in cardiovascular emergencies, an interventional cardiologist, and a clinical cardiologist expert in biostatistics. The DMC has experience in managing acute patients undergoing coronary revascularization and conducting a clinical trial. The DMC is responsible for monitoring the safety of participants and the conduct of the PROMISE trial. The DMC provides recommendations on the advisability of continuing the clinical trial or of adopting protocol changes necessary to maintain the safety of enrolled patients. The composition of the DMC will be defined before the start of the clinical trial. The initial DMC meeting will occur at the start of the trial and will convene once annually, to

examine the accumulated safety and enrollment data, review study progress, and discuss all the factors that might impact continuation of the study as designed.

**21.** It is the responsibility of the PI to report any changes in the research activity and unanticipated problems concerning the risk to human beings; including planned or untimely conclusion of the study and final report. Premature interruption of the study must be reported within 15 days. The regular term of the study will be communicated to AIFA (OsSC) and the CEC within 90 days. The final study report will be reported within 1 year of the end of the study.

## **22. Adverse events**

According to Article 2 of Directive 2001/20/EC “adverse event” is defined as follows:

‘Any untoward medical occurrence in a patient or clinical trial subject administered a medicinal product and which does not necessarily have a causal relationship with this treatment’.

“An adverse event can therefore be any unfavourable and unintended sign (including an abnormal laboratory finding, for example), symptom or disease temporally associated with the use of a medicinal product, whether or not considered related to the medicinal product”.

### **Adverse reactions**

An ‘adverse reaction’ is defined according to Article 2(n) of Directive 2001/20/EC as follows:

“All untoward and unintended responses to an investigational medicinal product related to any dose administered”.

The definition implies a reasonable possibility of a causal relationship between the event and the IMP.

### **Serious Adverse Events/Reactions (SAEs/SARs)**

A ‘serious adverse event/reactions’ is defined in Article 2 of Directive 2001/20/EC as follows:

“Any untoward medical occurrence or effect that at any dose results in death, is life-threatening, requires hospitalisation or prolongation of existing hospitalisation, results in persistent or significant disability or incapacity, or is a congenital anomaly or birth defect.

These characteristics/consequences have to be considered at the time of the event. For example, regarding a life-threatening event, this refers to an event in which the subject was at risk of death at the time of the event; it does not refer to an event which hypothetically might have caused death if it were more severe”.

Some medical events may jeopardise the subject or may require an intervention to prevent one of the above characteristics/consequences. Such events (hereinafter referred to as ‘important medical events’) should also be considered as ‘serious’ in accordance with the definition. Medical and scientific judgement should be exercised in deciding whether an event is ‘serious’ in accordance with these criteria.

Reports of serious adverse events (SAEs) must be immediately notified to the PI of the Coordinating Center regardless of the attribution by the Investigator of a causal relationship with the product under study.

The causal relationship with the product under study will be defined as follows:

- related: after careful evaluation, a safe relationship emerges with the use of the product under study,
- not related: due to causes not related to the product under study.

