### **23. Management and reporting of Serious Adverse Events/Reactions**

Any adverse event will be assessed, for

- seriousness, for serious adverse event and serious adverse reaction qualification,

- relatedness with the study drug (related/unrelated), for suspected adverse reaction, qualification
- expectedness, referring to safety reference document, and as per protocol, for suspected unexpected adverse drug reaction - SUSAR identification.

In accordance with Article 16 of Directive 2001/20/EC the investigator is responsible for reporting to PI of the Coordinating Centre all serious adverse events in relation to subjects treated by him in the clinical trial as it reads as follows:

“The investigator shall report all serious adverse events immediately to the sponsor except for those that the protocol or investigator’s brochure identifies as not requiring immediate reporting.”.

Moreover, any related or possibly related or unrelated Serious Adverse Events occurring during the clinical study should be immediately reported to the PI of the study coordinating center within a 24 hours following knowledge of the serious adverse event. Immediate reporting should allow to take the appropriate measures to address potential new risks in a clinical trial. The Investigator will always provide an assessment of causality between the experimental drug/event. It is mandatory for the Principal Investigator (and/or designees) to notify fatal events to the applicable EC.

The communication must be sent via email using the Serious Adverse Events form from the investigators involved in the study.

The form must be sent via email to the following recipient:

- Attention of [name] [name]: email: [[contact]](mailto:[contact])

It will be the responsibility of the PI of the coordinating center of the study to follow up on the report by completing and sending the following forms to the Ethics Committees:

- INITIAL SAE REPORT from SAE occurred during the study to the Ethics Committees involved (included in the Investigator's Study File);
- Follow-up REPORT on additional information from the Center to the PI of the coordinating center and from this to the Ethics Committees involved (included in the Investigator's Study File);

- FINAL REPORT on the final and conclusive information to the Ministry from the Center to the PI of the Health Coordinating Center (AC) and to the Ethics Committees involved (included in the Investigator's Study File).

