Serious unexpected adverse drug reactions (SUSAR) will be reported to the Competent Authorities, via Eudravigilance and the Ethical Committee within 7 days for fatal and life-threatening SUSAR, 15 days for other SUSARs.

All serious adverse events, serious adverse reactions and SUSARs will be presented as listing and a Developmental Safety Annual Report – DSUR will be issued annually from the study approval lock date to AIFA (Agenzia Italiana del Farmaco) and to the applicable Ethics Committees.

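### The Section 22 rule for calling an event related sets a higher bar than the protocol's own reasonable-possibility standard and leaves possibly related events without a class, so some could miss expedited reporting.

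*Combined protocol and SAP*

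**What the plan says.** Three parts of the safety text bear on causality.

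- **Section 22, Adverse reactions.** After giving the Directive's definition, the protocol adds: "The definition implies a reasonable possibility of a causal relationship between the event and the IMP".
- **Section 22, Serious Adverse Events/Reactions.** This is the working rule for the investigator. It has two classes: "related: after careful evaluation, a safe relationship emerges with the use of the product under study", and "not related: due to causes not related to the product under study". It also requires immediate notification of serious events to the coordinating centre, "regardless of the attribution by the Investigator of a causal relationship with the product under study".
- **Section 23, Management and reporting.** Each event is assessed for seriousness, for "relatedness with the study drug (related/unrelated), for suspected adverse reaction, qualification", and for expectedness, so that SUSARs can be identified. The section then requires 24-hour reporting to the coordinating investigator of "any related or possibly related or unrelated Serious Adverse Events occurring during the clinical study". SUSARs go to the competent authorities and the ethics committee "within 7 days for fatal and life-threatening SUSAR, 15 days for other SUSARs".

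The Competent authorities paragraph of Section 24 restricts rapid reporting to unexpected reactions that are related to the study drugs. It leaves everything else to the annual safety report.

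**The concern.** Section 22 gives two thresholds for one decision. The definition of an adverse reaction rests on a reasonable possibility. The rule that the investigator applies asks for a relationship that emerges as *safe* after careful evaluation. The middle ground, where a drug cause is plausible but not established, meets neither of the two classes. Section 23 shows that such events are expected, because it names them, but it does not say on which side of the related/unrelated split they fall.

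What is at stake is the expedited report to the competent authority. That report depends on the event being recognised as a reaction related to the study drugs. With three centres enrolling (Section 9), different investigators could resolve the same ambiguity differently.

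**Working it through.** No arithmetic applies. The point depends on no rate, effect size, SD or sample size, and the plan states no figure to reproduce. The check is to follow one event through the text.

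**Test case.** A serious event, unexpected against the product information, for which a drug cause is reasonably possible but not established.

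1. **Is it an adverse reaction?** Under Section 22, Adverse reactions, yes: a reasonable possibility is enough.
2. **Is it unexpected?** Under Section 22, Unexpected adverse reactions, yes, by construction. That definition starts from the term adverse reaction, so it carries the standard of step 1.
3. **Is it related under the working rule?** On the wording of the rule, no. *Safe* could mean certain, secure or established. Each of these asks for more than a reasonable possibility, so the conflict does not depend on choosing among them. If *safe* has no clear meaning here, the trial has no usable definition of related.
4. **Is it not related under the working rule?** Not clearly. That class requires the event to be due to causes other than the product, which is a positive attribution that has not been made.
5. **What does Section 23 do with it?** Suspected reactions are qualified on a two-way scale. The phrase *possibly related* appears only in the sentence on 24-hour reporting to the coordinating investigator, with no definition and no assignment to either side.
6. **Which reporting route follows?** If the event is treated as related, it is a SUSAR and the 7- or 15-day limit applies. If it is not, Section 24 sends it to the annual safety report.

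Steps 1 and 2 point to expedited reporting. Step 3 points away from it, and steps 4 and 5 do not settle the matter. The route therefore depends on which sentence the assessor follows.

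**What does not depend on the classification.** Under Sections 22 and 23 every serious event goes to the coordinating investigator, within 24 hours, whatever its attributed cause. That investigator sends initial and follow-up reports to the ethics committees, and fatal events must be notified to the ethics committee. Section 23 also provides for listings of all serious events and an annual report to AIFA and the ethics committees. The exposed step is the expedited report to the competent authority.

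**The case against.** The strongest case on the other side has four parts.

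- **The text can be read so that nothing is lost.** The definitions of adverse reaction and unexpected adverse reaction in Section 22 are operative text, and Section 23 speaks of a *suspected* reaction, which is less than certainty. An assessor who follows them could properly expedite a possible reaction. This stands, and it is why the conclusion is that such an event *could* miss the expedited route. It does not remove the conflict, because the only explicit definition of *related* points the other way. No sentence says that the coordinating centre reassesses causality on the lower standard.
- **Reading *safe* as *certain* is an inference.** This is correct. The documents do not say so, and the word looks like a translation. The direction of the conflict does not rest on it, as step 3 of the working shows.
- **Other safeguards limit the harm.** They do, for collection of events and for notice to ethics committees. The DMC also reviews accumulated safety data once a year. None of these supplies a causality standard for the expedited report.
- **The drugs are established.** Section 11a says that they are widely used and will be given within their approved indications. The documents give no rate for unexpected, only possibly related events, so no frequency can be claimed.

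Two stronger readings are tempting, and the documents support neither. A reader might infer that every event judged possible drops out of the SUSAR pathway. The rule does not say that: it leaves such events unclassified and does not place them under *not related*. A reader might also infer that counts of related events will be biased low in both arms. Section 20 plans no analysis of such counts, Section 23 plans only listings, and no endpoint in Section 12 uses relatedness.

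**Conclusion.** The point holds as an inconsistency in the safety-reporting text. The working definition of *related* in Section 22 is stricter than the standard which that section adopts for an adverse reaction, and events with a plausible but unproven drug cause have no class. The consequence is confined to one path: a serious, unexpected, possibly related event could miss the 7- or 15-day report to the authorities and appear only in annual reporting.

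The size cannot be computed from the documents. Sample size, power, alpha and the primary endpoint are not touched. The conclusion assumes only that *safe* means something stronger than reasonably possible; that it stands for *certain* is likely but not needed. The change should be made, because it is cheap and concerns participant safety, but it does not put the trial's main result in question.

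**What to change.** 1. In Section 22, replace the two causality classes with ones based on the standard already adopted there. For example: *related: a causal link with the study product is reasonably possible; not related: no such link is reasonably possible.*
2. In Section 23, state that *possibly related* is handled as *related* for SUSAR assessment.
3. Check that the use of *related* in the Competent authorities paragraph of Section 24 is read under the same definition, and that the options on the serious adverse event form match. The form is not in the documents and may already offer the right options.

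The cost is two sentences in the protocol and, if needed, one option on the form. The downside is possibly a few more expedited reports. No treatment, assessment schedule or analysis changes.

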### **Unexpected adverse reactions**

An unexpected adverse reaction is defined by the Article 2(p) of Directive 2001/20/EC as follows:

“An adverse reaction, the nature or severity of which is not consistent with the applicable product information (e.g. investigator’s brochure for an unauthorised investigational product or summary of product characteristics for an authorised product)”.

### **23. Management and reporting of Serious Adverse Events/Reactions**

Any adverse event will be assessed, for

- seriousness, for serious adverse event and serious adverse reaction qualification,

- relatedness with the study drug (related/unrelated), for suspected adverse reaction, qualification
- expectedness, referring to safety reference document, and as per protocol, for suspected unexpected adverse drug reaction - SUSAR identification.

In accordance with Article 16 of Directive 2001/20/EC the investigator is responsible for reporting to PI of the Coordinating Centre all serious adverse events in relation to subjects treated by him in the clinical trial as it reads as follows:

“The investigator shall report all serious adverse events immediately to the sponsor except for those that the protocol or investigator’s brochure identifies as not requiring immediate reporting.”.

Moreover, any related or possibly related or unrelated Serious Adverse Events occurring during the clinical study should be immediately reported to the PI of the study coordinating center within a 24 hours following knowledge of the serious adverse event. Immediate reporting should allow to take the appropriate measures to address potential new risks in a clinical trial. The Investigator will always provide an assessment of causality between the experimental drug/event. It is mandatory for the Principal Investigator (and/or designees) to notify fatal events to the applicable EC.

The communication must be sent via email using the Serious Adverse Events form from the investigators involved in the study.

The form must be sent via email to the following recipient:

- Attention of [name] [name]: email: [[contact]](mailto:[contact])

It will be the responsibility of the PI of the coordinating center of the study to follow up on the report by completing and sending the following forms to the Ethics Committees:

- INITIAL SAE REPORT from SAE occurred during the study to the Ethics Committees involved (included in the Investigator's Study File);
- Follow-up REPORT on additional information from the Center to the PI of the coordinating center and from this to the Ethics Committees involved (included in the Investigator's Study File);

- FINAL REPORT on the final and conclusive information to the Ministry from the Center to the PI of the Health Coordinating Center (AC) and to the Ethics Committees involved (included in the Investigator's Study File).

Serious unexpected adverse drug reactions (SUSAR) will be reported to the Competent Authorities, via Eudravigilance and the Ethical Committee within 7 days for fatal and life-threatening SUSAR, 15 days for other SUSARs.

All serious adverse events, serious adverse reactions and SUSARs will be presented as listing and a Developmental Safety Annual Report – DSUR will be issued annually from the study approval lock date to AIFA (Agenzia Italiana del Farmaco) and to the applicable Ethics Committees.

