
**6.c** There is a limited agreement regarding the acute and long-term medical management of patients with MINOCA. The results of a large observational study of MINOCA patients from the

SWEDHEART registry have shown a significantly lower rate of cardiovascular events associated with the use of statins and ACEi/ARB, a trend for a lower event rate with the use of  $\beta$ -blockers, while dual antiplatelet therapy (DAPT), a cornerstone of therapy for MICAD patients, failed to improve prognosis. An important limitation of this study is the heterogeneous nature of MINOCA cohort, without discerning the mechanism leading to myocardial infarction. Given these therapeutic shortcomings in this evolving area of clinical research, multicentre randomized clinical trials are needed to determine the optimal medical therapy for MINOCA based on the specific cause of the syndrome. Importantly, a precision-medicine approach had already proved its effectiveness in patients with stable angina and/or signs of ischemia but no obstructive coronary artery disease (INOCA). Indeed, the CorMicA trial showed that in patients with INOCA a strategy of adjunctive invasive testing for disorders of coronary function linked with stratified medical therapy led to improvements in patient outcomes, including reduction in angina severity and better quality of life. Similarly, the identification of functional alterations of coronary circulation is relevant in the clinical setting of MINOCA. We previously demonstrated that MINOCA patients with a positive test result (epicardial or microvascular spasm) had a significantly higher occurrence of cardiovascular events, thus identifying a high-risk subset of patients that may need a more aggressive therapy and a closer follow-up.

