## 7. Study objectives:

Primary objectives:

- To test if a precision-medicine approach with a careful investigation of the MINOCA aetiology and consequent aetiology-based treatment may result in improved quality of life outcomes.

Secondary objectives:

- To evaluate if the use of a precision-medicine approach with a specific therapy tailored on the MINOCA pathogenic mechanism will improve the prognosis.
- To assess if a precision-medicine approach with a careful investigation of the MINOCA aetiology and consequent aetiology-based treatment may result in reducing healthcare related costs.
- To test wherever a plasma circulating biomarker profile may be able to differentiate between the different causes of MINOCA, helping to identify the underlying pathophysiological mechanisms and to stratify prognosis and response to medical therapy.
- To test wherever cardiac magnetic resonance (CMR) may provide a morphological and functional cardiac characterization as well as help in the prognostic stratification in MINOCA.

**8. Study design:** Randomized multicenter prospective superiority phase IV trial comparing “precision medicine approach” *versus* “standard of care” in improving the prognosis and/or the quality-of-life of patients presenting with MINOCA. Patients will be randomized 1:1 to “precision medicine approach” vs “standard approach”.

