### **11a. Intervention(s):**

Patients with myocardial infarction undergoing to clinically indicated coronary angiography will be asked to sign the informed consent to the study before the coronary angiography/ventriculography and enrolled only after MINOCA diagnosis. MINOCA patients will be then randomized 1:1 (using an online software available 24h/24h) to:

**A. "Precision medicine approach"** consisting of:

*Comprehensive diagnostic work-up with:*

- Coronary angiography and ventriculography in all patients
- OCT (if coronary plaque rupture/erosion is suspected) at the time of coronary angiography in the cath-lab.
- Acetylcholine provocative test (to assess the presence of coronary vasospasm) at the time of coronary angiography in the cath-lab.
- TE-Echo and/or CE-Echo (if distal/microvascular embolization is suspected) during the hospitalization at the echo laboratory
- Blood sampling for circulating biomarkers and miRNA expression profile at the time of coronary angiography or within 12 hours from coronary angiography. Blood sampling will be processed and analysed in the research laboratory of the Department of Cardiovascular Science. Biological aliquots will be preserved at XBiogem Biobank at Fondazione Policlinico Universitario A. Gemelli IRCCS, Rome.
- Trans-thoracic echocardiography in all patients during the index hospitalization
- CMR in all cases during the index hospitalization.

*Targeted pharmacological treatment specific for the underlying cause:*

- DAPT ± stent implantation (if required), statins, beta-blockers, ACEi/ARB (in case of evidence of plaque rupture/erosion)
- CCB and/or nitrates (in case of documentation of coronary vasospasm)
- Anticoagulation (in case of coronary embolism).

**B. "Standard approach"** consisting of:

*Routine diagnostic work-up with:*

- Coronary angiography and ventriculography
- Transthoracic echocardiography in all patients during the index hospitalization
- CMR with contrast media only if clinically indicated (i.e. to exclude myocarditis or takotsubo syndrome)

*Standard medical treatment with:*

- DAPT in all patients
- Beta-blockers (if indicated by the clinical context, i.e. documentation of left ventricular ejection fraction <50%, tachycardia).

- High intensity statins in all patients
- ACEi/ARB (if clinically indicated).

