## **12. Outcomes of interests:**

Primary endpoints:

- Angina status and quality of life (evaluated using the Seattle Angina Questionnaire [SAQ]) at 1-year follow-up in patients with MINOCA.

[figure not shown]
\* To reduce the risk of detection and performance bias, a team of 2 cardiologists blinded to group allocation and belonging to an external cardiology unit will submit and collate the questionnaires from study participants.

Secondary endpoints:

- Rates of major adverse cardiovascular events (MACE; composite of all-cause mortality; re-hospitalization for myocardial infarction, stroke or heart failure; repeated coronary angiography) at 1-year follow-up in MINOCA patients.
- Healthcare primary and secondary related-costs (including costs for tests, procedures and outpatient visits or medicines) and socioeconomic burden of MINOCA patients.
- Ability of different circulating biomarkers (ET-1, NPY, CRP, sCD40L and miRNA [miR-16, miR-26a, miR-145, miR-222, miR-155-5p, miR-483-5p and miR-451]) as diagnostic biomarker and stratification tool for specific causes of MINOCA.
- Ability of CMR in evaluating different mechanisms of MINOCA and their prognostic value.

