### *Definition of the MACE*

MACE analysis includes:

- All cause death:
  - Cardiac death (in which a direct cause attributable to cardiac disease is present);
  - Sudden cardiac death (in which cardiac death occurred out of the hospital and suddenly; or in the hospital due to ventricular arrhythmias unrelated to other concomitant cardiac conditions);
  - Non-cardiac death (in which the event of death is considered not to be a direct consequence of cardiac disease);
- Hospitalization in which the main diagnosis is myocardial infarction, stroke or heart failure;
- Repeated coronary angiography.

The analysis will consider time to first event and time to each event.

Safety parameters will include data deriving from history and physical examination performed at each visit, laboratory data and results of functional and imaging tests. To enhance detection of adverse events between visits, all patients will be encouraged to contact the research team at any time with concerns or any perceived changes in their healthcare status.

**14. Sample size calculation:** Sample size calculation for the primary endpoint: to detect a mean group difference of change in SAQ score of 9 U, we calculated that a sample size of 70 patients per group (140 patients total) gave 80% power to detect a between-group difference in SAQ. This

calculation assumed a 2-tailed 5% significance level. This projected calculation assumed an SD of 19 U and was consistent with previous studies (see landmark CorMicA trial). However, we extended the sample size at 180 patients to avoid any reduction of statistical power due to patients lost at follow-up or due to poor compliance to medical therapy.

**15. Timeline:** At 36 months all patients will be enrolled and will have completed the follow-up. The study will be considered ended after the date of last patient last visit (LPLV). Blood samples will be analysed for assessment of circulating biomarkers and miRNA to detect associations with specific mechanisms underlying MINOCA, for stratification of prognosis and to evaluate response to medical therapy. Furthermore, CMR sequences will be analysed to detect functional and structural characteristics associated with specific mechanisms underlying MINOCA and with for stratification of prognosis.

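### The arms differ by rule in DAPT and anticoagulation, but apart from fatal bleeds and hospitalised strokes, bleeding is in no endpoint, has no definition and has no planned by-arm summary

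*Combined protocol and SAP*

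**What the plan says.** - **Treatment rules (section 11a).** The standard arm receives "DAPT in all patients". In the precision arm, DAPT heads a line that continues with "statins, beta-blockers, ACEi/ARB (in case of evidence of plaque rupture/erosion"), and a separate line gives "Anticoagulation (in case of coronary embolism"). The standard-arm list has no anticoagulation item.
- **Objective (section 7).** A secondary objective is to learn whether "a specific therapy tailored on the MINOCA pathogenic mechanism will improve the prognosis".
- **Endpoint (section 12).** The clinical-event endpoint for that objective is one-year MACE: "composite of all-cause mortality; re-hospitalization for myocardial infarction, stroke or heart failure; repeated coronary angiography". The section on the definition of MACE counts non-cardiac as well as cardiac death. It describes the hospital component as "Hospitalization in which the main diagnosis is myocardial infarction, stroke or heart failure", without limiting stroke to the ischaemic type.
- **Bleeding.** No primary or secondary endpoint names it, and there is no definition, grading scale or adjudication. The word appears once, as a possible complication of transoesophageal echocardiography.
- **Safety data.** The schedule of assessments marks adverse events at day 0 and at all four follow-up contacts. The DMC looks at accumulated safety data once a year. Section 23 says: "All serious adverse events, serious adverse reactions and SUSARs will be presented as listing", and adds an annual safety report. Section 20 compares categorical outcomes by Fisher exact test with relative risks, but mentions neither adverse events nor bleeding.

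**The concern.** The strategy under test changes who is assigned antiplatelet and anticoagulant drugs, so a reader will want to see bleeding by arm next to MACE. As planned, a non-fatal gastrointestinal or access-site bleed, even one that needs admission, contributes to no endpoint. It would appear as a line in a listing if serious, and otherwise as an adverse-event record with no stated summary. A listing gives neither a between-arm difference nor its uncertainty.

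The risk is to the secondary conclusion on prognosis. If MACE were similar in the two arms, or slightly lower in one, the report could make a statement about prognosis with most non-fatal bleeding absent from the planned comparison. A definition chosen after the data are seen would be weaker, because the trial is open label and three of its four follow-up contacts are telephone interviews.

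**Working it through.** **1. The plan's own figure.** Section 14 gives 70 per group for a SAQ difference of 9 with SD 19, two-sided 5%, 80% power.

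n = 2 × (1.960 + 0.842)² × 19² / 9² = 2 × 7.849 × 361 / 81 = 69.96, so 70. This reproduces. The total of 180 at 1:1 gives 90 per arm, the denominator used below. The sample size was set for SAQ only; neither MACE nor any safety outcome was sized.

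**2. What MACE captures.**

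| Type of bleed | Counted in MACE? | Why |
|---|---|---|
| Fatal | Yes | All-cause death, non-cardiac included |
| Non-fatal haemorrhagic stroke, hospitalised | Yes | Stroke type is not restricted |
| Other non-fatal, hospitalised | No | Main diagnosis is not MI, stroke or heart failure |
| Other non-fatal, not hospitalised | No | No matching component |

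**3. Size of the DAPT contrast.** Assigned by rule: 90 of 90 in the standard arm, 90 × f in the precision arm, where f is the share with plaque rupture or erosion. The documents do not give f. The range below is assumed, and patients without a plaque finding are counted as not assigned DAPT.

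| f (assumed) | Precision arm on DAPT | Gap |
|---|---|---|
| 20% | 18 of 90 | 72 |
| 40% | 36 of 90 | 54 |
| 60% | 54 of 90 | 36 |

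**4. What a by-arm estimate could show.** The documents give no bleeding rates, so all rates here are assumptions. The half-width of the 95% CI for the risk difference is 1.96 × √[p₁(1−p₁)/90 + p₂(1−p₂)/90]. For 4% versus 2% that is 1.96 × √(0.0384/90 + 0.0196/90) = 1.96 × 0.0254 = 0.050. Fisher power is exact: the summed binomial probability of all tables with p ≤ 0.05. The last column is the usual normal-approximation sample size with pooled variance under the null.

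| Standard vs precision | Expected patients | CI half-width | Fisher power | n per arm for 80% |
|---|---|---|---|---|
| 2% vs 1% | 1.8 vs 0.9 | ±3.5 points | 0.4% | 2319 |
| 4% vs 2% | 3.6 vs 1.8 | ±5.0 points | 3.4% | 1141 |
| 6% vs 3% | 5.4 vs 2.7 | ±6.0 points | 7.6% | 749 |
| 10% vs 5% | 9.0 vs 4.5 | ±7.7 points | 17.1% | 435 |

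With no events among 90 patients, the one-sided 95% upper bound is 1 − 0.05^(1/90) = 3.3%.

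**5. Illustration with invented counts.** Suppose 2/90 (precision) versus 5/90 (standard). RR = 0.40; SE(log RR) = √(1/2 − 1/90 + 1/5 − 1/90) = 0.823; 95% CI 0.08 to 2.01. The interval is wide, but it tells the reader what the data can and cannot exclude.

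**The case against.** Several points on the other side stand.

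- A reader might infer that MACE sees only ischaemic events and no non-fatal bleeding. The text does not support that. Stroke is unrestricted, non-cardiac death counts, and heart-failure admission and repeat angiography are not purely ischaemic.
- A reader might infer that the protocol itself identifies bleeding as the price of DAPT, because section 6.c says "dual antiplatelet therapy (DAPT), a cornerstone of therapy for MICAD patients, failed to improve prognosis". That sentence reports an observational registry, whose mixed mechanisms the protocol notes as a limitation, and it says nothing about bleeding.
- Section 23 concerns safety reporting. It does not say that serious events will only ever be listed, and the rule in section 20 could be applied to them. That is fair, but neither section commits to doing so, and the DMC's yearly review does not commit the final report to a by-arm estimate.
- The contrast in drugs actually taken may be smaller than the rules suggest. Section 11a states no regimen for precision patients in whom no mechanism is found, and section 11.c bars no concomitant medication.
- The comparison is badly underpowered, so a claim that bleeding would overturn the conclusion on prognosis goes too far.
- Grading takes some work. Scheduled laboratory data stop at day 0, and the blinded external team handles only the questionnaires.

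**Conclusion.** The point holds as a gap in the secondary and safety analyses. Antithrombotic assignment differs by rule. Outside fatal bleeds and hospitalised strokes, bleeding is undefined, is not an endpoint and has no stated by-arm summary. A conclusion on prognosis from MACE alone would omit most non-fatal bleeding.

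The size of the DAPT gap (72 to 36 of 90 patients) rests on an assumed plaque share of 20% to 60%. The precision and power figures rest on assumed bleeding rates. The documents supply neither. They also do not support saying that a bleeding difference will occur, which way it would go, or that this trial could confirm one. The change is worth making but not critical, because prognosis is a secondary objective and the primary SAQ result does not depend on it.

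**What to change.** - **Section 12:** add bleeding as a descriptive secondary safety outcome. Name one published graded definition and apply it to the adverse-event and hospital records already collected from T0 to T4. Limit the grades to those that these records can support.
- **Section 20:** state that bleeding and all serious adverse events will be tabulated by randomised arm, with the number of patients affected, a relative risk or risk difference and a 95% CI, placed beside the MACE results, with listings as supplementary. State that this is estimation only and not a powered test.
- **Section 23:** the reporting duties can stay as they are.

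**Cost:** one graded field on the existing adverse-event eCRF page, two tables, and some work to obtain and grade records, for which section 18 already asks sites to hold supporting documents such as discharge sheets and laboratory results. No new visit or test is needed.

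**Limits that remain:** intervals will be wide at 90 per arm, and reporting is open label and partly by telephone, so milder bleeds may be captured unevenly.
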